5. Subjects must be randomized within 28 days after signing the ICF; the first dose of study drug should be administered within 2 days after randomization.
6. CBC and chemistries do not have to be repeated if Screening tests are completed within 7 days of start of treatment.
7. Samples will be collected pre-dose, and at 1, 2 and 4 hours (± 10 minutes) post-dose.
8. PT, aPTT, INR.
9. Vital signs will include systolic and diastolic blood pressure, body temperature, pulse rate, body weight, and height (Week 1 only). Vital signs should be completed prior to treatment administration.
10. WOCBP only. Pregnancy test after randomization should be completed as deemed necessary by the Investigator or required by local law.
11. IMO-2125 should be administered prior to ipilimumab.
12. During the IMO Maintenance Period, all CTCAE Grade ≥ 2 irAEs and laboratory abnormalities (regardless of relationship to study drug) should be monitored until resolution, stabilization, or return to baseline. During the Follow-up Periods, for 90 days after the last dose of study treatment, all SAEs, irAEs, AEs Grade ≥ 3 , and associated concomitant medications for their treatment must be reported. For the remainder of the Follow-up Periods, AE reporting should be limited to Treatment-related Grade ≥ 3 AEs and SAEs, and the associated concomitant medications.
13. Blood samples for evaluation of plasma IMO-2125 concentrations will be collected pre-dose and at 1, 2, and 4 h post-dose (± 30 minutes) at Week 1 and Week 11 only.
14. Serum samples will be collected for analysis of anti-IMO-2125 and anti-ipilimumab antibodies; details are provided in the Laboratory Manual. Baseline sample to be collected at Week 1 before the first dose of study treatment.
15. Optional (see Laboratory Manual).
16. To inform treatment management decisions, disease assessments are to be completed at Week 12 (± 1 week), then every 8 weeks (± 2 weeks) for the first year and every 12 weeks (± 2 weeks) during subsequent years.
17. To minimize bias in the PRO data, disease and PRO assessments are to be completed prior to study drug administration and AE evaluations at Weeks 1, 8, and 12 (± 1 week), then every 8 weeks (± 2 weeks) for the first year and every 12 weeks (± 2 weeks) during subsequent years.
18. Per institutional practices following the frequency of active follow-up disease assessments.

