As of the 05 January 2017 data cut-off, 13 subjects have received IMO-2125 in planned escalating dose cohorts of 4, 8, 16, and 32 mg along with ipilimumab, and another 3 subjects have received 8 mg of IMO-2125 with pembrolizumab (dose escalation is ongoing). Treatment has been generally well-tolerated, with no dose-limiting toxicity observed in any dose cohort to date. One (8%) subject in the 4 mg IMO-2125 + ipilimumab group died due to progressive disease (PD) during the study follow-up period, approximately 5 months after completing all study treatment. Seven (54%) subjects have reported serious adverse events (SAEs); however, none of the SAEs were considered treatment-related by the Investigator. The most commonly reported treatment-emergent adverse events (TEAEs; reported in >5 subjects overall) for the IMO-2125 + ipilimumab combination are anemia, pyrexia, nausea, and vomiting. Four instances of potential immune-related toxicity have been observed: hypophysitis (2 events), adrenal insufficiency, and autoimmune hepatitis, the latter occurring in a subject who had previously experienced dose-limiting immune-related hepatitis while receiving ipilimumab monotherapy (in violation of the protocol eligibility criteria). The outcome for these subjects has been good with routine supportive measures ([Uemera 2017](#)).

Clinical activity is promising with 3 investigator-reported responses, including 1 complete response (CR). Tumor biopsies obtained showed maturation of myeloid DC1 subset in the IMO-2125 injected lesion 24 hrs post-treatment compared with pre-treatment biopsy ([Uemera 2017](#)).

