## **11.6 ADVERSE EVENTS OF SPECIAL INTEREST**

Systemic injection and infusion reaction such as cytokine release syndrome (CRS), anaphylactic and anaphylactoid reactions are deemed to be adverse events of special interest

Idera Pharmaceuticals, Inc.  
 Statistical Analysis Plan  
 Protocol Number: 2125-MEL-301

(AESIs). From communication with U.S. Food and Drug Administration (FDA) on 11 September 2020, the agency agreed with the Sponsor regarding the use of the American Society for Transplantation and Cellular Therapy (ASTCT) Consensus (Lee, 2019) for assessment of CRS events, and FDA’s guidance for the industry for immunogenicity assessment for evaluation of anaphylactic events. FDA recommended to assess any fever (not attributable to any other cause), hypotension and hypoxia, and to include related organ toxicities associated with CRS with severity graded according to CTCAE 4.03. FDA also recommended to include definitions of CRS, anaphylaxis, and hypersensitivity based on clinical diagnostic criteria and to provide an analysis based on the clinical criteria to distinguish CRS from anaphylaxis and hypersensitivity by presenting data on the nature, onset, frequency and severity, information about dose modifications and any evidence of recurrence with dose reduction or after drug withdrawal.

The Sponsor has used the following nine MedDRA LLTs for the initial database search for AESIs reported within 14 days after any tilso injections: anaphylaxis, cytokine release syndrome, infusion related reaction, injection site allergic reaction, injection related reaction, allergic reaction, anaphylactic reaction, anaphylactoid reaction, or systemic inflammatory response syndrome. A listing of AEs corresponding to these LLTs was generated to be used for evaluation against the ASTCT definition for CRS as well as the FDA guidance document on anaphylactic reaction which are provided below as a reference:

AE Term	Definition
CRS	A supraphysiologic response following any immune therapy that results in the activation or engagement of endogenous or infused T cells and/or other immune effector cells. A qualified CRS event will include fever along with hypotension and/or hypoxia.
Fever	A disorder characterized by elevation of the body’s temperature above the upper limit of normal, and a temperature of 38.0 °C is considered grade 1 fever.
Hypotension	A disorder characterized by a blood pressure that is below the normal expected for an individual in a given environment.

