Hypoxia	An Oxygen saturation (SaO 2 ) <94% or an individual requiring supplemental oxygen to correct a deficit in oxygenation is considered to have hypoxia. Oxygen provided only as a comfort measure should not be used.
Anaphylactic reaction	Anaphylaxis is a serious, acute allergic reaction without a particular immunologic mechanism and based on the following clinical features: 
 
1. Acute onset of an illness (minutes to several hours) with involvement of the skin, mucosal tissue, or both, and at least one of the following:               
 
• Hypoxia
 
• Hypotension
 
 
 
2. Two or more of the following that occur rapidly after exposure to Tilsotolimod (minutes to several hours):               
 
• Involvement of the skin-mucosal tissue
 
 
 

Idera Pharmaceuticals, Inc.  
 Statistical Analysis Plan  
 Protocol Number: 2125-MEL-301

AE Term	Definition
	
 
• Hypoxia
 
• Hypotension
 
• Persistent gastrointestinal symptoms
 

	
 
3. Hypotension after exposure to Tilsotolimod when prior systemic reactions with Tilsotolimod has occurred (minutes to several hours)
 

In order to perform a more comprehensive assessment of the AESIs, a search of all TEAEs which are coded under any of the following MedDRA SOC and started within 14 days after any tilsotolimod injections will also be conducted:

- General disorders and administration site condition
- Respiratory and mediastinal disorders vascular disorders
- Immune system disorders (see [Table 2](#) in Section 11.5)

The AEs identified will be reviewed and classified by the Sponsor as CRS, anaphylactic reaction or hypersensitivity reaction. The classification will be imported into the analysis dataset for summaries.

Significant AESIs will be summarized, that include Grade 3 and above systemic injection and infusion reactions.

Based on the strategy and definitions stated above, these AEs included under each event type will be determined based on a programmatic search of the AE datasets using the specified LLT in conjunction of a medical review of the AEs identified. The incidence of the AESIs under each event type will be summarized by MedDRA preferred term.

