14.3.6.1 Treatment-Emergent Adverse Events Leading to Permanent Discontinuation of IMO-2125 by Preferred Term, Safety Set	IDMC, ORR, Final
14.3.6.2 IMO-2125-Related Treatment-Emergent Adverse Events Leading to Permanent Discontinuation of IMO-2125 by Preferred Term, Safety Set	ORR, Final
14.3.6.3 Treatment-Emergent Adverse Events Leading to Permanent Discontinuation of Ipilimumab by Preferred Term, Safety Set	IDMC, ORR, Final
14.3.6.4 Ipilimumab-Related Treatment-Emergent Adverse Events Leading to Permanent Discontinuation of Ipilimumab by Preferred Term, Safety Set	ORR, Final
14.3.6.5 Immune-Related Treatment-Emergent Adverse Events Leading to Permanent Discontinuation of IMO-2125 by Preferred Term, Safety Set	ORR, Final
14.3.6.6 Immune-Related Treatment-Emergent Adverse Events Leading to Permanent Discontinuation of Ipilimumab by Preferred Term, Safety Set	ORR, Final
14.3.7.1 Significant Treatment-Emergent Adverse Events by Preferred Term, Safety Set	ORR, Final
14.3.7.2 Time to Onset of Significant Treatment-Emergent Adverse Events, Safety Set	ORR, Final
14.3.8.1 Summary of Change from Baseline in Hematology, Safety Set	ORR, Final
14.3.8.2 Summary of Change from Baseline in Chemistry, Safety Set	ORR, Final
14.3.8.3 Summary of Change from Baseline in Coagulation, Safety Set	ORR, Final
14.3.8.4 Summary of Change from Baseline in Complement, Safety Set	ORR, Final
14.3.8.5 Summary of CTCAE Shifts from Baseline Grade in Hematology, Safety Set	IDMC, ORR, Final
14.3.8.6 Summary of CTCAE Shifts from Baseline Grade in Chemistry, Safety Set	IDMC, ORR, Final

Idera Pharmaceuticals, Inc.  
 Statistical Analysis Plan  
 Protocol Number: 2125-MEL-301

Table Title	Timing of Analysis
14.3.8.7 Summary of Shifts from Baseline Relative to the Normal Range in Selected Laboratory Tests, Safety Set	ORR, Final
14.3.9.1 Summary of Shifts in Blood Pressure from Baseline to Worst Case Post-Baseline, Safety Set	IDMC, ORR, Final
14.3.9.2 Summary of Shifts in Heart Rate and Temperature from Baseline to Lowest and Highest Post-Baseline, Safety Set	IDMC, ORR, Final
14.3.9.3 Summary of ECG Values by Visit, Safety Set	ORR, Final
14.3.9.4 Summary of Shifts in QTcF from Baseline from the Highest Post-Baseline, Safety Set	ORR, Final
14.3.9.5 Summary of QTcF Increase from Baseline from the Highest Post-Baseline, Safety Set	IDMC, ORR, Final
14.4.1 Summary of Pharmacokinetic Concentrations, PK Analysis Set	ORR, Final

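### SAP 11.6 promises AESI summaries with no grade limit, but every AESI output it names is labelled 'Significant' (Grade 3 and above), so Grade 1-2 reactions and isolated post-injection fever have no clear AESI output

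*SAP*

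**What the plan says.** SAP 11.6 treats systemic injection and infusion reactions, including CRS and anaphylaxis, as AESIs. It reports that FDA accepted the ASTCT consensus for assessing CRS. It then adds: "FDA recommended to assess any fever (not attributable to any other cause), hypotension and hypoxia, and to include related organ toxicities associated with CRS". CTCAE version 4.03 is named as the grading scale. It also records that FDA wanted an analysis separating CRS from anaphylaxis and hypersensitivity, with data on frequency and severity among other things.

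The definitions table says of CRS: "A qualified CRS event will include fever along with hypotension and/or hypoxia". The same table counts 38.0 °C as grade 1 fever.

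Events are found by two searches covering 14 days after an injection: nine MedDRA lowest-level terms, then all treatment-emergent events in listed system organ classes. Neither search has a minimum grade. The sponsor classifies what is found into three types: CRS, anaphylaxis or hypersensitivity.

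On reporting, one sentence reads: "Significant AESIs will be summarized, that include Grade 3 and above systemic injection and infusion reactions". Other sentences in the section promise incidence by event type and preferred term, a Kaplan-Meier analysis of time to first onset, and a listing with a grade column. None of these three carries a grade limit. The outputs named at the end of 11.6 are all titled 'Significant'. So are those in SAP 16.2, for example "14.3.7.1 Significant Treatment-Emergent Adverse Events by Preferred Term, Safety Set".

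**The concern.** The promises in the text and the named outputs cover different sets of events. Programming usually follows the output list. If it does here, the AESI tables would hold Grade 3 and above only, and could not show how often these reactions occur across grades. Isolated unexplained fever, which FDA is said to have wanted assessed, would have no place in the AESI reporting at any grade. For a drug given to stimulate cytokine release, a reader of the study report could take an almost empty AESI table as evidence that reactions are rare, when it reflects only how the table was restricted.

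**Working it through.** There is no plan figure to reproduce and no arithmetic in the point itself. The check sets the passages side by side.

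| Item | Promise in the text of SAP 11.6 | Named output (11.6 and 16.2) |
|---|---|---|
| Incidence by event type and preferred term | AESIs, no grade limit | Table 14.3.7.1, titled 'Significant' |
| Time to first onset | AESIs, no grade limit | Table 14.3.7.2, titled 'Significant' |
| Subject listing | AESIs, with a grade column | Listing 16.2.3.2.9, titled 'Significant' |

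(The listing number 16.2.3.2.9 is also given to the immune-related listing, so the AESI listing must be identified by its title.)

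**What 'Significant' means.** The only explanation is the sentence tying it to Grade 3 and above systemic injection and infusion reactions. The section opens by describing AESIs as that same class of reactions, so the restriction would apply to all AESIs and not to a subset.

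**Three illustrative subjects, each with an event a few days after an injection:**

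1. *Grade 3 event classified as CRS.* It appears in all three AESI outputs on either reading.
2. *Grade 2 event classified as CRS, anaphylaxis or hypersensitivity.* The searches can find it, since they have no grade floor. Under the text it belongs in all three outputs. Under the titles, read with the Grade 3 sentence, it belongs in none.
3. *Unexplained fever of 38.0 °C, alone.* It is not CRS, because hypotension or hypoxia is required. It does not meet the anaphylaxis features in the table. Hypersensitivity has no definition there, so that route is open but unguided. Isolated hypoxia is in the same position. So is isolated hypotension, unless an earlier systemic reaction brings it under the third anaphylaxis criterion.

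**Where subjects 2 and 3 do appear.** SAP 11.2 and 16.2 tabulate all-grade treatment-emergent events by preferred term (Table 14.3.2.2.2) and by maximum grade (Table 14.3.2.4.1). Section 11.9.1 gives temperature and blood pressure shifts, and section 8.3.3 includes a category of 38 °C and above. None of these applies the 14-day window after each injection or the event-type classification. The onset table (14.3.4) uses 3-week intervals from first dose, not time since an injection.

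**Comparison within the SAP.** Immune-related events have all-grade, maximum-grade and Grade 3+ tables (14.3.2.6.1 to 14.3.2.6.3). The fuller format is therefore already in use for another class of special events.

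**The case against.** The best defence has four parts.

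- *The text already promises all grades, and the Grade 3 sentence says 'include', not 'only'.* This is correct, and it is why the point is an internal contradiction and not a plan to suppress low grades. SAP section 3 says the mock displays are in separate documents, so the shells may resolve it. The SAP itself does not.
- *Low-grade events are summarised.* This stands: they are in the general tables and shifts listed above. A reader might infer that they go unreported, and the documents do not support that. What is missing is their reporting as AESIs. The shifts are a partial substitute, because for scheduled readings "Vital signs should be completed prior to treatment administration". Fever in the hours after an injection would reach them mainly through unscheduled readings.
- *FDA accepted the CRS framework.* This also stands. A reader might infer that FDA asked for fever alone to count as CRS, or for a low-grade table. The SAP reports neither. It reports a recommendation to assess such fever and to present frequency and severity. Whether the SAP definition matches the ASTCT consensus cannot be checked from these documents.
- *Detection does not depend on scheduled vital signs.* It is tempting to say that pre-dose readings, with no scheduled oxygen saturation, mean CRS will seldom be captured. The documents do not support this. AESIs come from adverse event records and medical review, events are assessed continuously (Protocol 10.1), and subjects are observed for at least 30 minutes after each injection (Protocol 9.3.3.2).

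All safety analyses are descriptive, so no hypothesis test depends on the outcome.

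**Conclusion.** The point holds as a contradiction between the text of SAP 11.6 and its named outputs, together with a missing AESI category for isolated fever, hypotension and hypoxia (subject to the anaphylaxis exception above). It affects two tables and one listing. It rests on two assumptions: that outputs are built from the list in 16.2, and that 'Significant' is read as Grade 3 and above, the only meaning given.

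The number of subjects affected cannot be derived. The documents do show that fever is common: in Study 2125-204, the events reported in more than 5 subjects "for the IMO-2125 + ipilimumab combination are anemia, pyrexia, nausea, and vomiting" (Protocol 4.3.2.1). With 13 combination subjects that is at least 6/13 = 46%. A reader might scale this to Arm B: an assumed 30% to 50% of 454/2 = 227 subjects gives 68 to 114. That range is not a count of omitted AESIs. The 6/13 covers fever of any cause in dose cohorts from 4 to 32 mg, without the 14-day window, and the 30% to 50% is an assumption. Nor do the documents support a forecast that the tables would show almost no CRS.

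This is a worthwhile, inexpensive correction to safety reporting with no bearing on the primary endpoints.

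**What to change.** In SAP 11.6 and 16.2:

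1. Produce Tables 14.3.7.1 and 14.3.7.2 and the AESI listing for all grades by event type, with the incidence table also by maximum grade. Show Grade 3+ as sub-rows, and retitle the outputs to match. If 'Significant' is kept as a label for the sub-rows, define it.
2. Leave the CRS definition unchanged.
3. Add a descriptive row for fever (38.0 °C or above with no other cause), hypotension and hypoxia reported as adverse events within 14 days of an injection and not meeting the CRS definition. Events already counted as anaphylaxis or hypersensitivity stay under those types.

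The cost is SAP wording, revised shells, extra table rows and more sponsor medical review, chiefly to judge whether a fever has another cause. The searches already have no grade floor, so no new data are needed and no visit or treatment changes.

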**Table 2 List of MedDRA SOCs Used by Sponsor in Identification of Additional Potential irAEs**

MedDRA SOCs
Cardiac disorders
Endocrine disorders
Eye disorders
Gastrointestinal disorders
General disorders and administration site conditions
Hepatobiliary disorders
Immune system disorders
Injury, poisoning and procedural complications
Investigations
Musculoskeletal and connective tissue disorders
Neoplasms benign, malignant and unspecified (incl cysts and polyps)
Product issues
Renal and urinary disorders
Respiratory, thoracic and mediastinal disorders
Skin and subcutaneous tissue disorders
Surgical and medical procedures
Vascular disorders

The number and percentage of subjects who experienced at least one irAE will be tabulated. The preferred terms will be identified using the search strategy as described above. The frequency and percentage of immune-related TEAEs will be summarized by PT, as well as by PT and maximum grade. Similar analyses will be repeated for Grade 3 or above immune-related TEAEs and for Grade 3 or above treatment-related immune-related TEAEs. The frequency and percentage of treatment-related immune-related TEAEs will be summarized by PT and maximum grade.

Similarly, the frequency and percentage of immune-related serious TEAEs will be summarized by PT and maximum grade. Similar analysis will be repeated for Grade 3 or above immune-related serious TEAEs by PT. The number and percentage subjects who experienced immune-related TEAEs leading to permanent discontinuation of IMO-2125 and

Idera Pharmaceuticals, Inc.  
 Statistical Analysis Plan  
 Protocol Number: 2125-MEL-301

---

subjects who experienced immune-related TEAEs leading to permanent discontinuation of ipilimumab will be presented by PT.

A listing of immune-modulating medications which include thyroid hormone replacement therapies, systemic steroid and immuno-suppressants used after occurrence of irAE will be presented. Thyroid hormone replacement therapies will be identified by WHO drug ATC prefix H03, systemic steroids by WHO drug ATC prefix H02, and immuno-suppressants by WHO drug ATC prefix L04.

All irAEs will be listed. This listing will include treatment arm, age, sex, verbatim term and the corresponding coded terms, start date and study day, end date and study day, grade, serious (yes or no), relationship to treatment (yes or no), action taken, and outcome. It will also include an indicator for the source of the irAEs (CRF or sponsor-defined).

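### The supplementary AESI search in SAP 11.6 names neither the Skin nor the Gastrointestinal SOC, although the anaphylaxis criteria in the same section use both kinds of sign

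*SAP*

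**What the plan says.** SAP 11.6 identifies AESIs in three steps.

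1. An initial database search on nine MedDRA lowest-level terms (LLTs), among them anaphylaxis, cytokine release syndrome (CRS) and allergic reaction. It covers events reported within 14 days of an injection and has no SOC limit.
2. For wider coverage, "a search of all TEAEs which are coded under any of the following MedDRA SOC and started within 14 days after any tilsotolimod injections". The bullets beneath name the General SOC; a line reading "Respiratory and mediastinal disorders vascular disorders", taken here as two SOCs; and the Immune SOC, which carries a bracketed reference to Table 2 of SAP 11.5.
3. Classification: "The AEs identified will be reviewed and classified by the Sponsor as CRS, anaphylactic reaction or hypersensitivity reaction".

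The anaphylaxis definition has three criteria. Criterion 1 is an acute illness with "involvement of the skin, mucosal tissue" or both, plus hypoxia or hypotension. Criterion 2 is two or more of four signs after exposure: skin-mucosal involvement, hypoxia, hypotension, and "Persistent gastrointestinal symptoms". Criterion 3 is "Hypotension after exposure to Tilsotolimod when prior systemic reactions with Tilsotolimod has occurred".

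Table 2 of SAP 11.5 lists 17 SOCs used to find potential immune-related AEs (irAEs). They include "Skin and subcutaneous tissue disorders" and "Gastrointestinal disorders". SAP 11.5 has the irAE review weigh each event against dosing and against other AEs at about the same time. SAP 11.6 has no equivalent sentence.

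**The concern.** A reaction recorded under a reaction diagnosis is already caught by the nine LLTs. What the SOC search adds is reactions entered as separate signs, and there the list leaves out the SOCs for two of the four signs in criterion 2. SAP 11.6 also records that FDA recommended an analysis on clinical criteria to separate CRS from anaphylaxis and hypersensitivity. A search that does not clearly collect the signs those criteria use can fall short of that.

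At stake is whether an event meeting the SAP's own definition of anaphylaxis reaches the sponsor's reviewers. The risk is a foreseen one: Protocol Table 3 gives anaphylaxis as its example of a life-threatening AE that ends IMO-2125 treatment.

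**Working it through.** The plan states no figure to reproduce. The check compares the search list with the criteria and then counts sign patterns.

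**Does the Table 2 pointer close the gap?** The pointer follows the Immune bullet. Table 2 already contains all four SOCs named in 11.6 (General, Respiratory, Vascular, Immune), so if the pointer meant the whole table, the separate bullets would be redundant. The table's title also ties it to irAEs. On the other hand, a single SOC needs no table reference, so the narrow reading leaves the pointer without a purpose. The text is unclear; it cannot be relied on to bring in Skin and GI.

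**Which patterns are retrieved?** Assumption, since the documents give no coding: hypoxia codes to Respiratory, hypotension to Vascular, and skin and GI signs to their own SOCs. The retrieved signs are then hypoxia and hypotension only.

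Four signs give 2^4 = 16 subsets. Criterion 2 needs at least two signs: 6 pairs + 4 triples + 1 quadruple = 11 patterns. Criterion 1 is already contained in these. With a prior systemic reaction, criterion 3 adds hypotension alone, giving 12.

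| | No prior reaction | Prior reaction |
|---|---|---|
| Qualifying patterns | 11 | 12 |
| Not retrieved (skin-mucosal + GI only) | 1 | 1 |
| Retrieved, criteria met on retrieved signs alone | 4 | 8 |
| Retrieved, but a skin or GI sign is needed to meet the criteria | 6 | 3 |

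The 4 are the patterns with both hypoxia and hypotension. The 8 are all those containing hypotension. The 3 are hypoxia without hypotension, joined by skin, GI or both.

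**Range.** Keep hypoxia and hypotension coded as assumed. If General or Immune terms brought in every skin and GI sign, 0 patterns would go unretrieved; if they brought in none, 1 would. These are unweighted patterns, and no patient count can be derived.

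**What each change does, under the same assumption.** Patterns that can be confirmed:

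| Change | No prior reaction | Prior reaction |
|---|---|---|
| Criteria applied to all of a subject's AEs, list as written | 10 of 11 | 11 of 12 |
| One of the two SOCs added, retrieved signs only | 8 of 11 | 10 of 12 |
| Both SOCs added, retrieved signs only | 11 of 11 | 12 of 12 |

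**How wide is the search window?** Injections are at Weeks 1, 2, 3, 5, 8, 11, 16, 20 and 24. Taking Week w to start on day 7(w − 1) + 1, these are days 1, 8, 15, 29, 50, 71, 106, 134 and 162. Counting the injection day and the next 14 days, the first four windows merge into days 1–43 (43 days). The other five are separate, 5 × 15 = 75 days. Total: 43 + 75 = 118 of the first 176 days, or 67%.

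**The case against.** The strongest reply is that silence is not a restriction. SAP 11.6 plans a medical review against clinical criteria, and its AESI listing has a column for related organ toxicities, so reviewers are expected to look past the triggering term. This largely stands. A reader might infer from the table that 1 + 6 = 7 of 11 patterns would be lost. The documents do not support that: the six surface through hypoxia or hypotension and fail only if the reviewer ignores the subject's other AEs, which the SAP does not say. The reply does not rescue the one unretrieved pattern, because both the review and the listing start from events or subjects already identified.

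Other safeguards narrow the gap further.

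- Protocol 10.1.3.1 asks sites to report an integrated diagnosis where possible.
- Subjects are observed for at least 30 minutes after each IMO-2125 dose (Protocol 9.3.3.2).
- A life-threatening reaction is an SAE, reported on a form with a narrative. SAP 11.3 and 11.4 list all SAEs and all TEAEs leading to discontinuation.
- The irAE review in SAP 11.5 covers Skin and GI events relative to dosing, although for a different purpose.

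The AESI summaries and listing named in SAP 11.6 are all titled as Significant, a class described there as including Grade 3 and above. The section also promises incidence by event type, but the output list in SAP 16.2 shows no separate all-grade AESI table. If Significant means Grade 3 or above, the visible gap shrinks to severe reactions of this one pattern.

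Finally, the breadth of a SOC search is partly a matter of preference, and wider SOCs bring noise. That is a fair cost, but the mismatch here is with the section's own criteria.

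A reader might also infer that skin-only hypersensitivity reactions are missed. SAP 11.6 gives no criteria for hypersensitivity, so that cannot be tested.

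**Conclusion.** The point holds and is minor. The search list in SAP 11.6 does not match the signs in its own anaphylaxis definition. Under the stated coding assumption, one qualifying pattern is not retrieved: skin-mucosal plus GI signs, with neither hypoxia nor hypotension, entered separately and not under any of the nine LLTs. With different coding of skin and GI signs, that could fall to none. For the remaining patterns the SAP leaves open whether concurrent AEs are consulted, which is a matter to clarify and not evidence of loss.

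The effect is confined to AESI case-finding, mainly in the outputs titled as Significant. It would be wrong to infer that such events drop out of safety reporting, since all TEAEs and SAEs are still tabulated. The ORR and OS analyses are untouched.

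**What to change.** In SAP 11.6, before the classification is imported into the analysis dataset:

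- add "Skin and subcutaneous tissue disorders" and "Gastrointestinal disorders" to the SOC list;
- list Respiratory and Vascular as two separate SOCs;
- say what the Table 2 reference covers;
- state that the CRS and anaphylaxis criteria are applied to all of a subject's AEs in the same post-injection window, in line with the irAE review in SAP 11.5.

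The SOC additions retrieve the missing pattern. The last item settles how the other patterns are judged and reduces dependence on where a particular mucosal sign is coded. None of this changes which events meet the CRS definition; it would show where the anaphylaxis criteria are met as well.

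The cost is SAP wording and a longer candidate listing for a medical review already planned. The extra load is real. The windows cover about two thirds of the first 176 days, Protocol 4.3.2.1 reports nausea and vomiting among the commonest TEAEs of the combination, and non-specific terms such as rash would also be drawn in.
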